4.5.12.6 Withdrawal from the Roche Clinical Repository

Patients who give consent to provide RCR specimens have the right to withdraw their specimens from the RCR at any time for any reason. If a patient wishes to withdraw consent to the testing of his or her specimens, the investigator must inform the Medical Monitor in writing of the patient's wishes through use of the RCR Subject Withdrawal Form and, if the trial is ongoing, must enter the date of withdrawal on the RCR Research Sample Withdrawal of Informed Consent eCRF. The patient will be provided with instructions on how to withdraw consent after the trial is closed. A patient's withdrawal from Study GO29058 does not, by itself, constitute withdrawal of specimens from the RCR. Likewise, a patient's withdrawal from the RCR does not constitute withdrawal from Study GO29058.

4.5.12.7 Monitoring and Oversight

RCR specimens will be tracked in a manner consistent with Good Clinical Practice by a quality-controlled, auditable, and appropriately validated laboratory information

management system, to ensure compliance with data confidentiality as well as adherence to authorized use of specimens as specified in this protocol and in the Informed Consent Form. Roche monitors and auditors will have direct access to appropriate parts of records relating to patient participation in the RCR for the purposes of verifying the data provided to Roche. The site will permit monitoring, audits, IRB or EC review, and health authority inspections by providing direct access to source data and documents related to the RCR samples.

4.6 PATIENT, TREATMENT, STUDY, AND SITE DISCONTINUATION

4.6.1 Patient Discontinuation

Patients have the right to voluntarily withdraw from study drug or withdraw from the study at any time for any reason. In addition, the investigator has the right to withdraw a patient from the study at any time. Reasons for withdrawal from the study may include, but are not limited to, the following:

- Patient withdrawal of consent at any time
- Any medical condition that the investigator or Sponsor determines may jeopardize the patient's safety if the patient continues in the study
- Investigator or Sponsor determines it is in the best interest of the patient
- Patient non-compliance, defined as failure to comply with the protocol requirements for assessments of safety and efficacy of the study medications, as well as failure to comply with study drug administration.

Every effort should be made to obtain information on patients who withdraw from the study. The primary reason for withdrawal from the study should be documented on the appropriate eCRF. However, patients will not be followed for any reason after consent has been withdrawn. *Until approximately the end of August 2018, patients who withdraw from study drug may decide to continue on study to allow follow-up for survival.* Patients who withdraw from the study will not be replaced.

4.6.2 Study Drug(s) Discontinuation

Patients must discontinue study drugs if they experience any of the following:

- Any medical condition that the investigator or Sponsor determines may jeopardize the patient's safety if the patient continues to receive study drug(s)
- *Disease progression (as assessed by the investigator)*
- Unacceptable toxicity
- Non-compliance with protocol specified drug administration and follow-up tests

The primary reason for study treatment discontinuation should be documented on the appropriate eCRF. Patients who discontinue study treatment will not be replaced.

4.6.3 Study and Site Discontinuation

The Sponsor has the right to terminate this study at any time. Reasons for terminating the study may include but are not limited to the following:

- The incidence or severity of adverse events in this or other studies indicates a potential health hazard to patients.
- Patient enrollment is unsatisfactory.

The Sponsor will notify the investigator if the Sponsor decides to discontinue the study.

The Sponsor has the right to close a site at any time. Reasons for closing a site may include but are not limited to the following:

- Excessively slow recruitment
- Poor protocol adherence
- Inaccurate or incomplete data recording
- Non-compliance with the International Conference on Harmonisation (ICH) guidelines for Good Clinical Practice
- No study activity (i.e., all patients have completed and all obligations have been fulfilled)

5. ASSESSMENT OF SAFETY

5.1 SAFETY PLAN

Taselisib is not approved and is currently in clinical development. Thus, the entire safety profile is not known at this time. The safety plan for this study is designed to ensure patient safety and will include specific eligibility criteria and appropriate safety assessments.

5.1.1 Management of Selected Toxicities Observed with Taselisib in Clinical Studies

Experience with PI3K inhibitors to date has demonstrated that the agents are generally well-tolerated. Common adverse events seen in ongoing clinical trials that are testing PI3K inhibitors include fatigue, diarrhea, skin rash, altered taste, pneumonitis, and hyperglycemia. In general, these agents appear to be reasonably well-tolerated at doses examined to date without irreversible and/or intolerable toxicities.

The toxicities observed with taselisib are consistent with those observed with other PI3K inhibitors. Selected toxicities of interest for taselisib include gastrointestinal toxicities, pneumonitis, rash, stomatitis, and hyperglycemia. Certain adverse events (e.g., rash, colitis, and pneumonitis) may also occur within 4 weeks of holding or stopping taselisib. On the basis of prior clinical experience with the taselisib and fulvestrant combination, some patients have continued to derive clinical benefit with single-agent fulvestrant even after discontinuation of taselisib. Therefore, in some cases per

investigator assessment, fulvestrant dosing may be continued while taselisib or placebo is being held or discontinued (e.g., for adverse events). The fulvestrant dose level should not be modified.

5.1.1.1 Dose Modification of Taselisib/Placebo due to Toxicity

The taselisib or placebo dose reduction instructions provided in [Table 2](#) are intended to serve as recommended guidelines to allow ongoing treatment for patients experiencing clinical benefit without signs or symptoms of progression while monitoring patient safety. In addition to these guidelines, more conservative drug interruptions or dose reductions for the management of adverse events are permitted at the discretion of the investigator when deemed to be in the best interest of the patient.

Due to the approximately 40-hour half-life for taselisib, investigators should consider holding taselisib or placebo for certain Grade 2 toxicities until the adverse events resolve to Grade ≤ 1 as discussed below (e.g., stomatitis, oral mucositis, rash, diarrhea). Certain toxicities may occur or worsen within 4 weeks of holding or discontinuing taselisib (e.g., pneumonitis, colitis, rash). These adverse events may eventually resolve but also may require the use of corticosteroids. Investigators should follow management guidelines for toxicities as described below, including administration of topical or systemic corticosteroids as appropriate.

Table 2 Overall Dose Modification Guideline for Taselisib-Related Adverse Events

	Taselisib/Placebo
Starting dose	4 mg QD
First reduction	2 mg QD
Second reduction	2 mg QOD ^a

QD=once daily; QOD=every other day.

^a If the patient continues to experience specified drug-related adverse events after the second dose reduction, taselisib/placebo should be discontinued.

The investigator may temporarily suspend taselisib/placebo dosing in the patient due to a taselisib-related toxicity or an unanticipated medical event not associated with study treatment toxicity or with disease progression. Depending on the nature and the severity of the taselisib-related toxicity, the investigator may resume taselisib/placebo dosing in the patient at the same dose or at one dose level lower (as detailed in [Tables 3–8](#)).

5.1.1.1.1 Gastrointestinal Toxicity

Nausea, vomiting, *dyspepsia*, diarrhea, stomatitis, and oral mucositis have been observed in patients who receive taselisib. Colitis was diagnosed by several methods, including endoscopy and abdominal imaging (CT scans). Pathology from biopsies obtained from endoscopy confirmed colitis. Patients usually present with Grade 2 or Grade 3 diarrhea that has been refractory to antidiarrheal agents. The time (from the

first dose of study treatment) to onset (formal diagnosis of colitis) ranged from approximately 2–8 months. Patients had resolution or improvement of gastrointestinal toxicities upon holding study drug and/or initiating corticosteroid therapy. Perforated duodenal ulcer was observed in 2 patients (1 patient at 6-mg capsule dose in combination with letrozole; another patient at 6-mg capsule dose in combination with fulvestrant). Appropriate caution should be taken with the administration of medications such as aspirin, NSAIDs, and corticosteroids, which can increase the risk of gastritis, peptic ulcers, or gastrointestinal perforation.

Patients with inflammatory bowel disease, such as Crohn's disease or ulcerative colitis, are excluded from this study. Patients who resume taselisib/placebo treatment should be monitored closely for signs of renewed diarrhea.

Dose delay and modification guidelines for patients who experience gastrointestinal toxicities (diarrhea, colitis, stomatitis and oral mucositis) can be found in [Table 3](#) and [Table 4](#).

Table 3 Management Guidelines for Diarrhea and Colitis

Grade	Taselisib/Placebo Dose Modification and Management
1	
Manage per standard-of-care with anti-diarrheal agents^a (e.g., loperamide)
 
For Grade 1 diarrhea occurring after Cycle 2 that persists > 5 days despite treatment with anti-diarrheal agents, obtain stool culture for infectious workup^b. Infections (e.g., Clostridium difficile, enteric bacteria, CMV) should be treated with the appropriate antibiotic.
 
For non-infectious diarrhea, consider holding taselisib/placebo and treating with a corticosteroid taper (20–40 mg prednisone PO QD starting dose) or budesonide 9 mg PO QD. Upon completion of corticosteroid treatment, resume taselisib/placebo dosing at same dose or one dose level lower per investigator evaluation.
 
(Note: Table continued on next page)

2	
Hold taselisib/placebo and initially manage with anti-diarrheal agents^a. Obtain stool culture for infectious workup^b. Infections (e.g., Clostridium difficile, enteric bacteria, CMV) should be treated with the appropriate antibiotic.
 
For non-infectious Grade 2 diarrhea that has not improved to Grade \leq 1 despite 48 hours of anti-diarrheal treatment or for Grade 2 colitis, treat with corticosteroid taper (20–40 mg prednisone PO QD starting dose) or budesonide 9 mg PO QD. Steroid dosage can be increased if diarrhea does not improve.
 
If diarrhea or colitis does not improve after 48 hours of corticosteroid treatment, a colonoscopy should be considered to evaluate for other causes of diarrhea (e.g., CMV colitis).
 
If Grade 2 diarrhea occurred after Cycle 2 or improved with corticosteroid treatment or for Grade 2 colitis, resume taselisib/placebo dosing at one dose level lower upon improvement to Grade \leq 1 and after completion of any corticosteroid taper.
 
If Grade 2 diarrhea occurred before Cycle 2 and did not require corticosteroid treatment, resume taselisib/placebo dosing at the same dose level or one dose level lower per investigator evaluation upon improvement to Grade \leq 1.
 
For recurrent Grade 2 diarrhea, resume taselisib/placebo dosing at one dose level lower upon improvement to Grade \leq 1. For patients with a second Grade 2 diarrhea event that is confirmed to be infectious on the basis of results from the stool culture, taselisib/placebo may be resumed at the same dose level if approved by the Medical Monitor.

Table 3 Management Guidelines for Diarrhea and Colitis (cont.)

Grade	Taselisib/Placebo Dose Modification and Management
3	
Hold taselisib/placebo dosing and initially manage with anti-diarrheal agents^a. Obtain stool culture for infectious workup^b. Infections (e.g., Clostridium difficile, enteric bacteria, CMV) should be treated with the appropriate antibiotic.
 
For Grade 3 diarrhea or colitis, treat with systemic corticosteroids (IV solumedrol 16–20 mg every 8 hours or prednisone 60–80 mg PO QD equivalent to start). Can increase steroid dosage if diarrhea does not improve.
 
Consider colonoscopy as part of further gastrointestinal workup. If diarrhea does not improve after 48 hours of corticosteroid treatment, a colonoscopy should be considered to evaluate for other causes of diarrhea (e.g., CMV colitis).
 
If diarrhea or colitis improves to Grade ≤ 1 and upon completion of any steroid taper, resume taselisib/placebo dosing at one dose level lower. For patients with Grade 3 diarrhea that is confirmed to be infectious on the basis of results from the stool culture, taselisib/placebo may be resumed at the same dose level if approved by the Medical Monitor.
 
Patients with recurrent Grade 3 diarrhea or colitis must be permanently discontinued from taselisib/placebo.

4	
Permanently discontinue taselisib/placebo. Manage as per Grade 3 diarrhea guidelines.

IV = intravenous; PO = taken by mouth; QD = once daily.

^a Suggested anti-diarrheal medications include the following:

- Loperamide (initial: 4 mg, followed by 2 mg after each loose stool, up to 16 mg/day)
- Diphenoxylate and atropine (diphenoxylate 5 mg, four times daily, until control achieved [maximum: 20 mg/day], then reduce dose as needed; some patients may achieve control with doses of 5 mg/day)
- Tincture of opium (6 mg of undiluted opium tincture [10 mg/mL] four times daily).

^b Non-infectious diarrhea can be diagnosed by stool culture with work-up for *Clostridium difficile* and for various enteric bacteria. Fecal calprotectin is a possible marker for bowel inflammation. Blood-based cytomegalovirus polymerase chain reaction test can also be used to detect cytomegalovirus infection.

Table 4 Management Guidelines for Stomatitis and Oral Mucositis

Grade	Taselisib/Placebo Dose Modification and Management Guidelines
All grades	Aggressive mouth care that includes mouthwash formulations (e.g., combinations of local anesthetic, antihistamine, corticosteroid, antacid, anti-fungal and/or antibiotics) may be implemented to help manage symptoms Diet management (e.g., avoidance of spicy foods)
1	Monitor symptoms and initiate management (see above). Re-evaluate within 48–72 hours.
2	Hold tselisib/placebo, and manage until Grade ≤ 1 . If stomatitis or mucositis improves to Grade ≤ 1 , resume tselisib/placebo dosing at the same dose or one dose level lower per investigator evaluation. For recurrent Grade 2 stomatitis or mucositis, resume tselisib/placebo dosing at one dose level lower.
3	Hold tselisib/placebo and manage until Grade ≤ 1 . If stomatitis or mucositis improves to Grade ≤ 1 , resume tselisib/placebo dosing at one dose level lower.
4	Permanently discontinue tselisib/placebo.

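### Table 3 directs systemic corticosteroids for Grade 3 (and so Grade 4) diarrhea without the non-infectious condition that it sets for diarrhea at Grades 1 and 2

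*Combined protocol and SAP*

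**What the plan says.** All of the text is in Table 3 of protocol Section 5.1.1.1.1.

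- **Grade 1.** Diarrhea after Cycle 2 that persists beyond 5 days on anti-diarrheals gets a stool culture. Steroids then come in for one group: "For non-infectious diarrhea, consider holding taselisib/placebo and treating with a corticosteroid taper".
- **Grade 2.** The study drug is held, anti-diarrheals are started and a stool culture is taken. The steroid instruction opens "For non-infectious Grade 2 diarrhea that has not improved" after 48 hours of anti-diarrheal treatment. It also covers Grade 2 colitis, with no infection condition attached to the colitis part.
- **Grade 3.** The drug is held, anti-diarrheals are started, a stool culture is taken, and infections, including CMV, are treated. A separate instruction follows: "For Grade 3 diarrhea or colitis, treat with systemic corticosteroids", at IV solumedrol 16–20 mg every 8 hours or prednisone 60–80 mg daily to start, with increases allowed if there is no improvement. The row adds "Consider colonoscopy as part of further gastrointestinal workup", with no time condition. On restarting it makes special provision: "For patients with Grade 3 diarrhea that is confirmed to be infectious on the basis of results from the stool culture", the same dose level may be resumed if the Medical Monitor approves.
- **Grade 4.** "Permanently discontinue taselisib/placebo. Manage as per Grade 3 diarrhea guidelines".

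Footnote b describes the work-up that identifies non-infectious diarrhea and allows a blood CMV PCR.

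**The concern.** The table orders an infectious work-up at Grade 3 and expects that some results will be positive, but it does not say what a positive result means for steroids. In the two milder rows it does say so for diarrhea. A site that follows the rows literally could therefore treat the same confirmed infection without steroids at Grade 2 and with high-dose systemic steroids one grade higher.

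The stake is patient safety. Section 5.1.1.1.1 itself warns that corticosteroids raise the risk of gastritis, peptic ulcer and gastrointestinal perforation, so needless steroids carry a cost that the protocol recognises. Infection is also a realistic alternative diagnosis. Section 5.1.1.1.8 reports infections in 41.8% of taselisib patients against 23.9% of controls, and lists gastrointestinal tract infections among those common in the taselisib arm. Nothing in the statistical design depends on the point.

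**Working it through.** No plan figure rests on this text, so the check is a comparison of rows, a search for the condition elsewhere, and a count of the patients to whom such rows would apply.

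**1. Rows side by side, for steroids**

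| Grade | Diarrhea: infection condition? | Colitis: infection condition? | Starting steroid |
|---|---|---|---|
| 1 | Yes | Not addressed | Prednisone 20–40 mg taper, or budesonide 9 mg (to be considered) |
| 2 | Yes, plus 48 hours of failed anti-diarrheals | No | Prednisone 20–40 mg taper, or budesonide 9 mg |
| 3 | No | No | Prednisone 60–80 mg, or IV solumedrol |
| 4 | No (taken from Grade 3) | No (taken from Grade 3) | As Grade 3 |

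For diarrhea the condition is present in 2 of 4 rows and absent in 2 of 4. For colitis no row has it, so the inconsistency concerns diarrhea alone.

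**2. One patient through two rows.** Take culture-confirmed infectious diarrhea. At Grade 2 she falls outside the steroid sentence and gets the appropriate anti-infective. At Grade 3 she gets the same anti-infective and also falls inside the steroid sentence as written.

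**3. Is the condition supplied elsewhere?**

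- Section 5.1.1.1 leaves topical or systemic steroids to be given where suitable. It does not mention infection.
- The text before Table 3 asks for caution when giving corticosteroids. This applies at every grade but is not linked to a culture result.
- Section 5.1.1.1.8 asks for prompt, suitable treatment of a diagnosed infection and for consideration of holding or stopping study drug. It does not mention steroids.
- Table 5 (pneumonitis) makes steroids depend on excluding infection at Grades 2 to 4. Table 6 (rash) has no such condition at Grade 3. The protocol therefore has no uniform convention in either direction, and the point rests on Table 3 alone.

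**4. Whom the Grade 3 and 4 rows would govern.** Section 1.3.2 gives taselisib-related Grade 3–4 events in 83 patients on taselisib plus fulvestrant: diarrhea 8%, colitis 8%, enterocolitis 1%, CMV colitis 1%.

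- 8% means 7 patients: 7/83 = 8.4%, whereas 6/83 = 7.2% would round to 7% and 8/83 = 9.6% to 10%.
- 1% means 1 patient: 1/83 = 1.2%.
- Overlap between the terms is not given. With full overlap the count is 7, and 7/83 = 8.4%. With no overlap it is 7 + 7 + 1 + 1 = 16, and 16/83 = 19.3%.

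So 7 to 16 of 83 patients had events of the kind these rows address. The size of the gap itself would need the infectious share of Grade 3–4 diarrhea, steroid use in infected patients, and the number still on taselisib under Version 4. The documents give none of these.

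**The case against.** The strongest reply is that the Grade 3 row should be read in order and as a deliberate escalation. It starts with holding the drug, anti-diarrheals, culture and treatment of infection, and only then reaches steroids. Restarting follows "upon completion of any steroid taper", which suggests that not every Grade 3 patient is expected to have had steroids. The row also drops the 48-hour wait, raises the dose and brings colonoscopy forward. That pattern fits early empiric treatment of severe disease, in which waiting for a culture could do harm. The same section reports that gastrointestinal toxicities improved on holding drug, on corticosteroids, or on both. With the general caution on corticosteroids and the deference to clinical judgment, a competent investigator would probably reconsider steroids once a culture came back positive.

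Most of this stands. It is why the claim is that an infected patient *could* receive steroids, and why an empiric start is not criticised. What it does not answer is the next step. If empiric use is intended, the row does not say so, and it does not say whether steroids continue after a positive result. It uses that result for two other decisions, so adding the third would be natural.

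A reader might also infer that the table compels steroids in every confirmed infection. The order of the row, the softening wording and the general caution do not support that.

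**Conclusion.** The point holds in a narrow form. For diarrhea, Table 3 ties steroids to a non-infectious cause at Grades 1 and 2 but not at Grades 3 and 4, although the Grade 3 row anticipates confirmed infection. No other section supplies the missing link between the work-up result and the steroid decision. The conclusion assumes only that the rows are read as written; the Grade 3 row appears complete, so no redaction or extraction gap explains the difference. The range of 7 to 16 of 83 describes patients with relevant severe events, not infected or harmed patients.

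Three stronger inferences are not supported:

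- **That harm has occurred.** Section 5.1.1.1.1 reports perforated duodenal ulcer in 2 patients, Section 1.3.2 implies one Grade 3–4 CMV colitis, and Section 5.1.1.1.8 shows more infections on taselisib. None of these is linked to steroids given under Table 3.
- **That a protocol-wide rule is broken.** Table 6 shows there is no such rule.
- **That the milder rows are fully protected.** Grade 2 colitis is not.

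Severity is minor: a patient-safety clarification with no effect on endpoints, alpha or power.

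**What to change.** Keep the Grade 3 steroid sentence, so that empiric treatment of severe disease is not delayed, and add directly after it:

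*If the infectious work-up (footnote b) is positive, do not start corticosteroids, or re-evaluate and stop those started empirically, and treat the infection, unless the investigator judges that co-existing non-infectious colitis requires them.*

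Grade 4 takes this up through its cross-reference. The same sentence can be added to the Grade 2 row to cover Grade 2 colitis. This is better than placing a non-infectious qualifier before the combined Grade 3 phrase for diarrhea and colitis. That wording could be read as conditioning Grade 3 colitis while Grade 2 colitis stays unconditioned, which would create a new mismatch.

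The cost is one sentence in one row, or in two, issued as a clarification or with the next amendment. The stool culture is already ordered in both rows, and the other tests are named in footnote b. Steroids for severe colitis need not be delayed, because an empiric start remains allowed. No statistical section changes.
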